7.6. Stopping Rules

Following are the stopping rules for the Pilot portion of the study:

- If ≥ 2 of 6 patients experience DLTs in cohort 1 (1000 mg/day), Cohort -1 (800 mg per day) will be activated.
- If ≥ 2 of 6 patients in Cohort -1 experience DLTs, the study will be terminated due to intolerability.

Following are the stopping rules for the Phase II portion of the study:

- Subjects will be discontinued from the study for reasons of AE, clinically significant disease progression, patient request, investigator decision, protocol violation, patient noncompliance, and study termination by the Sponsor or institutional review board (IRB)/independent ethics committee (IEC). See Section 7.5 for guidance on dose reduction and discontinuation of therapy for safety concerns. Noncompliant patients may be replaced.

Patients will be discontinued from the study if they are off study drug for more than 2 weeks, regardless of the reason, unless the patient has demonstrated a clinical benefit from therapy and

would like to continue dosing with study drug after discussion between the investigator and the Sponsor.

The Pilot and Phase II portions of the study may be discontinued if the study is terminated by the Sponsor, the China Food and Drug Administration (CFDA), or other regulatory authorities.

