Based on the treatment emergent adverse event (TEAE) reports of increased INR observed in patients receiving concomitant warfarin, careful monitoring is required during treatment with pexidartinib. Warfarin doses should be adjusted if an increase in INR is noted.

Updated hepatic safety risk information as of December 2017; please consult the IB for more information: Hepatotoxicity is an important adverse drug reaction. Elevations of liver transaminases and bilirubin have been observed in studies with pexidartinib, together with cases of drug induced cholestasis. Cases of cholestasis have been observed in the first 8 weeks, have generally resolved with treatment discontinuation, but in some cases have been severe, with a protracted course requiring liver dialysis and, in 1 case, transplantation. Hepatotoxicity may be fatal. One fatal case with ongoing cholestatic liver injury at the time of death has been reported. Monitor patients closely as defined in the protocol. Protocol defined dose reductions and discontinuations of pexidartinib, increased frequency of laboratory monitoring, and reporting of findings should be followed (refer to Section 7.5). In addition, rechallenge with pexidartinib should not be attempted without prior discussion with the Sponsor's Medical Monitor.

Pexidartinib is a novel, orally active, small molecule inhibitor that targets CSF1R, Kit, and oncogenic Flt3, but remains highly selective versus other kinases. The potent inhibition of these 3 kinases can be exploited to attack tumors via multiple mechanisms. Pexidartinib has shown a potent inhibitor of the proliferation of these target dependent models.

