7.2 Dose Levels for Pilot Portion of the Study

7.2.1 Dose Evaluation

During the Pilot portion of the study, 3 to 6 patients in sequential dose cohorts will be enrolled. The dose cohorts are as follows:

- Cohort 1: 1000 mg/day (400 mg in the morning and 600 mg in the evening)
- Cohort -1(if required): 800 mg/day (400 mg BID)

Cohort -1 will be carried out only if Cohort 1 is considered intolerable. Study treatment may be delayed up to 2 weeks to permit resolution of any treatment-related toxicity outside the DLT window.

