7.5. Dose-Modification Guidelines

Toxicities that occur outside the DLT window will be taken into consideration when determining the RP2D. Reduction/interruption of dosing for AEs may take place at any time. Below are guidelines for dosage modification for PLX3397–related toxicities as well as guidelines for their management. Dose reductions should occur in increments of 200 mg/day, depending on the toxicity grade, as noted in [Table 7-1](#) and [Table 7-2](#).

These parameters are only a guide and are not intended to supersede the clinical judgment of the treating physician. Medical Monitor should be notified of any dose adjustments. Dosing interruptions longer than 2 weeks for any reason should generally result in discontinuation from the study, unless the patient has demonstrated a clinical benefit from therapy and would like to continue dosing with study drug after discussion between the investigator and the Sponsor. Rechallenge with a reduced dose of pexidartinib may result in a recurrence of increased serum transaminases, bilirubin, or ALP. Monitor liver tests weekly for the first month after rechallenge.

Table 7-1: Dose Modification Guidelines for Treatment-emergent Toxicities

Adverse Reaction	Severity	Pexidartinib Dosage Modifications
Increased ALT and/or AST	Greater than 3 to 5 times ULN	
 • Withhold and monitor liver tests weekly. • If AST and ALT are less than or equal to 3 times ULN within 4 weeks, resume at reduced dose. • If AST or ALT is not less than or equal to 3 times ULN in 4 weeks, permanently discontinue pexidartinib.

	Greater than 5 to 10 times ULN	
 Withhold and monitor liver tests twice weekly. If AST and ALT are less than or equal to 3 times ULN within 4 weeks, resume at reduced dose. If AST or ALT is not less than or equal to 3 times ULN in 4 weeks, permanently discontinue pexidartinib.
	Greater than 10 times ULN	
 Permanently discontinue pexidartinib. Monitor liver tests twice weekly until AST or ALT is less than or equal to 5 times ULN, then weekly until less than or equal to 3 times ULN.
Increased ALP and Gamma-glutamyl transpeptidase (GGT)	ALP greater than 2 times ULN with GGT greater than 2 times ULN	
 Permanently discontinue pexidartinib. Monitor liver tests twice weekly until ALP is less than or equal to 5 times ULN, then weekly until less than or equal to 2 times ULN.

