Increased bilirubin	Total bilirubin greater than ULN to less than 2 times ULN or Direct bilirubin greater than ULN and less than 1.5 times ULN	
 Withhold and monitor liver tests twice weekly. If an alternate cause for increased bilirubin is confirmed and bilirubin is less than ULN within 4 weeks, resume at reduced dose. If bilirubin is not less than ULN in 4 weeks, permanently discontinue pexidartinib.
	Total bilirubin greater or equal to 2 times ULN or Direct bilirubin greater than 1.5 times ULN	
 Permanently discontinue pexidartinib. Monitor liver tests twice weekly until bilirubin is less than or equal to ULN.
Adverse reactions or other laboratory abnormalities	Severe or intolerable	
 Withhold until improvement or resolution. Resume at a reduced dose upon improvement or resolution.

Table 7-2: Additional Liver Evaluation

Evaluation	Comments
Increase frequency of testing liver chemistries to twice per week, including INR, and continue until liver chemistries have stabilized, and then reduce to weekly until liver chemistries return to normal or baseline.	Investigational treatment may be started after liver function tests recover to Grade 0 to 1 or baseline level, and in consultation with Medical Monitor.

Detailed history focusing on medications and substances used: alcohol, change in medication dosages, new medications added, attention to use of acetaminophen, OTC medication use, and recreational drug use. Check for change in diet or use of dietary supplements, with particular attention to dose and duration of any herbal product.	Suspect medications will be discontinued or substituted for if possible.
Detailed medical history and physical examination seeking new abnormalities.	Evaluate abnormalities found.
Full serological evaluation for hepatitis A, B, C, and E (IgG and IgM). Check for autoimmune hepatitis with serological laboratory studies.	If viral hepatitis or autoimmune hepatitis suggested, have patient evaluated by hepatologist.
Liver ultrasound performed to evaluate liver and biliary tree.	Evaluate any abnormalities found.
Check history for exposure to chemical agents.	Remove chemical exposure and have patient seen by hepatologist.
Obtain hepatology consult if liver function continues to rise beyond 14 days.	Contact Medical Monitor.

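### Version 9.0's dosing text is inconsistent in three places (length of a liver hold, Table 7-3 at 1000 mg/day, restart level after a liver hold) and must be reconciled

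*Combined protocol and SAP*

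**What the plan says.** **Length of a liver hold.** For AST/ALT above 3x and up to 10x ULN, Table 7-1 in Section 7.5 says: "If AST and ALT are less than or equal to 3 times ULN within 4 weeks, resume at reduced dose". Its lower bilirubin row uses the same 4-week window. Section 7.6 and the synopsis stopping rules say: "Patients will be discontinued from the study if they are off study drug for more than 2 weeks, regardless of the reason". Both then exempt a patient with demonstrated clinical benefit who wishes to continue, after the investigator and Sponsor have discussed it. The text of Section 7.5 carries the same limit and exemption in softer words: "Dosing interruptions longer than 2 weeks for any reason should generally result in discontinuation from the study". Section 7.2.1 and the synopsis dosing row add: "Study treatment may be delayed up to 2 weeks to permit resolution of any treatment-related toxicity outside the DLT window". That sentence has no exemption.

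**Inhibitors.** Section 7.7.2 says to avoid moderate or strong CYP3A inhibitors and UGT inhibitors. Where that is impossible, the dose is to be cut as Table 7-3 sets out. The table lists current doses of 800, 600 and 400 mg/day. Cohort 1 is 1000 mg/day (Section 7.2.1), and Section 5.1 reports that six Pilot patients were enrolled and received that dose.

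**Restart level.** For transaminases Table 7-1 says: "If AST or ALT is not less than or equal to 3 times ULN in 4 weeks, permanently discontinue pexidartinib". For bilirubin it allows resumption only if another cause is confirmed and the value falls below ULN within 4 weeks, and says: "If bilirubin is not less than ULN in 4 weeks, permanently discontinue pexidartinib". Table 7-2 says treatment may be started once liver tests return to Grade 0 to 1 or to the baseline level, after consulting the Medical Monitor. Criterion 7b admits AST/ALT below 5x ULN with liver metastases, and total bilirubin up to 1.5x ULN.

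**The concern.** A site holding drug for a liver signal needs one answer to two questions: how long the hold may last, and what value permits restart. A site with a patient on an unavoidable inhibitor needs one dose. The documents give two answers to each of the first two questions for identifiable patients, and no answer to the third at the dose the study used.

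Liver injury is the drug's main hazard in this protocol: Section 3.3 warns that it can be fatal, and revising the dose modification criteria was a stated main purpose of Version 9.0. Two sites following the same protocol could therefore manage the same patient differently, and either could be recorded as a deviation.

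**Working it through.** No sample size, power or alpha figure is involved, so there is no stated figure to reproduce. The check sets the passages against each other, with arithmetic on their own limits.

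**1. Hold length**

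- Table 7-1 window: 4 x 7 = 28 days.
- Limit in Sections 7.5, 7.6 and 7.2.1 and the synopsis: 2 x 7 = 14 days.
- Difference: 28 - 14 = 14 days, that is days 15 to 28.

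Consider a patient whose AST and ALT return to 3x ULN or less on day 20 of the hold. Table 7-1 says resume at a reduced dose. Section 7.6 says the patient should already have been discontinued, unless benefit has been shown. Section 7.6 refers to Section 7.5 for safety guidance, but that does not settle the matter, because 7.5 contains both the 2-week sentence and the 4-week table.

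The exemption is hardest to use early. The first scheduled CT is at the end of Cycle 2: 2 x 28 / 7 = week 8. Section 3.3 places the observed cholestasis cases in the first 8 weeks. So at the time of greatest stated risk, benefit on the scheduled CT will normally not yet be available.

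**2. Table 7-3**

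| Current dose (mg/day) | Modified dose (mg/day) | Ratio | Difference (mg/day) |
|---|---|---|---|
| 800 | 400 | 50% | 400 |
| 600 | 400 | 67% | 200 |
| 400 | 200 | 50% | 200 |
| 1000 | no row | – | – |

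The missing row cannot be read off. Scaling 1000 mg by the table's ratios gives 500 or 667 mg/day, which is 2.5 or 3.3 capsules of 200 mg. Subtracting the table's differences gives 600 or 800 mg/day, depending on which row is followed. These figures show only that the table does not determine an answer; none is proposed.

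**3. Restart level**

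- AST/ALT: entry allowed below 5x ULN with liver metastases; Table 7-1 restart at 3x ULN or less. The tables conflict for entry values above 3x and below 5x ULN.
- Bilirubin: entry allowed up to 1.5x ULN; Table 7-1 restart below ULN with another cause confirmed. The tables conflict for entry values from ULN to 1.5x ULN. The separate Gilbert's allowance in 7b is in mg/dL and is left aside.

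Two illustrative courses, with values chosen here and direct bilirubin assumed not to trigger the higher row:

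| | Entry | On drug | Week 4 | Table 7-1 | Table 7-2 |
|---|---|---|---|---|---|
| ALT (x ULN) | 4 | 6 | 4 | Above 3: permanent stop | At baseline: may start |
| Bilirubin (x ULN) | 1.3 | 1.6 | 1.3 | Not below 1: permanent stop | At baseline: may start |

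This uses only the baseline route in Table 7-2. Whether its Grade 0 to 1 route also differs from 3x ULN for transaminases cannot be shown, because the documents do not give the CTCAE cut-offs.

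**4. Renal dose (clarification only)**

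Section 7.8 gives 200 + 400 = 600 mg/day for CLcr 15 to 89 mL/min. Criterion 7c admits CrCl above 60 mL/min, so patients above 60 and up to 89 fall under both. The renal dose is 600/1000 = 60% or 600/800 = 75% of the cohort doses, and Section 3.2 says doses under 800 mg/day are not to be considered in this study.

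**The case against.** **The 2-week and 4-week limits can be read together.** On this reading 2 weeks is the general rule, patients with benefit may go longer, and 4 weeks is the outer limit for liver events. Section 7.5 also says: "These parameters are only a guide and are not intended to supersede the clinical judgment of the treating physician". This stands for patients with demonstrated benefit, and extension subjects have stable disease or better by definition, so they may qualify. It does not cover a patient without demonstrated benefit. The guidance sentence appears in Section 7.5 but not in 7.6, 7.2.1 or the synopsis, and Section 3.3 points the other way: "Protocol defined dose reductions and discontinuations of pexidartinib, increased frequency of laboratory monitoring, and reporting of findings should be followed". Discussion with the Medical Monitor, requested during liver holds and required before rechallenge, does not decide which written limit applies.

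**Table 7-3 has a gap, not a contradiction, and the first instruction is to avoid inhibitors.** Correct, but the fallback instruction still cannot be followed at 1000 mg/day.

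**Table 7-2 concerns evaluation, and its restart remark is permissive.** It is a comment subject to consultation and could be read as additional to Table 7-1. Even so, Section 7.5 cites both tables for dose reductions, and permission to start cannot coexist with permanent discontinuation in the same patient.

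**Stronger readings a reader might infer, which the documents do not support:**

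- That the unexempted 2-week limit in Section 7.2.1 binds extension subjects. It sits under Pilot dose evaluation; carrying it over because the extension column is in the Pilot schedule (Table 2-1) is inference.
- That Section 7.8 contradicts eligibility or the cohort doses. Section 7.5 already allows individual reductions in 200 mg/day steps, and Section 3.2 can be read as being about cohort doses. What is missing is a statement of scope.
- That Tables 7-1 and 7-2 conflict on how often to test. Table 7-1 sets weekly tests at above 3 to 5x ULN and Table 7-2 twice per week, but Table 7-2 gives no trigger level, so no conflict is shown.

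**Conclusion.** The point holds in three places in current Version 9.0 text:

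1. Opposite instructions for 14 days of a liver hold (days 15 to 28) in a patient without demonstrated benefit.
2. No instruction in Table 7-3 at 1000 mg/day, the dose of all six enrolled patients.
3. Opposite restart instructions for patients admitted with AST/ALT above 3x and below 5x ULN, or bilirubin from ULN to 1.5x ULN.

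The overlap of Section 7.8 with criterion 7c is a minor matter of scope.

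Practical reach is narrow. The sponsor decided to discontinue the study after six Pilot patients. Section 5.1 reports two ongoing as of June 2018, and the documents do not say whether either was still on drug when Version 9.0 was dated (25 Jan 2020). Nor do they give those subjects' current dose, renal function, inhibitor use or baseline liver tests. A reader might infer that these two subjects were affected, or that DLT or response results were; neither is shown. No effect on power or on the analyses is shown. The case for correction is that the text governs continuing treatment with a drug whose liver toxicity can be fatal.

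**What to change.** The sponsor's clinical team should amend the protocol to reconcile:

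- the 2-week limits in Sections 7.2.1, 7.5 and 7.6 and the synopsis with the 4-week window in Table 7-1;
- Table 7-3 with the 1000 mg/day dose;
- Table 7-1 with Table 7-2 on the level that permits restart, for patients with raised values at entry.

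The amendment should state which of these rules apply in the extension phase. As a minor clarification, it should state the scope of Section 7.8 against criterion 7c, the 1000 and 800 mg/day cohort doses and Section 3.2. Which dose, hold length or restart level is right is a clinical decision, and none is proposed here.

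The cost is amendment wording and IRB/IEC approval. No new procedures, data or analyses are needed, and patient numbers, accrual and power do not change.

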7.7. Concomitant Medications (and Procedures)

Concomitant treatment is permitted if the medication is not expected to interfere with the evaluation of safety or efficacy of the study drug. During the study, if the use of any concomitant treatment becomes necessary (e.g., for treatment of an AE), the treatment must be recorded on the electronic case report form (eCRF), including the reason for treatment, generic name of the drug, dosage, route, and start and stop dates of administration.

For the purposes of determining the DLT in Cycle 1, the use of G-CSF or other hematologic growth factors is not permitted during Cycle 1. If a patient develops a protocol defined hematologic DLT and requires the use of G-CSF or other hematologic growth factors, they may be used in accordance with local standard of care.

Patients enrolled in studies with PLX3397 who are also receiving concomitant warfarin should have their anti-coagulation status carefully monitored, especially shortly after initiation of PLX3397, for the potential need to make adjustments in warfarin dosing. In particular, INR should be obtained just prior to initiation of PLX3397, within 1 to 2 weeks after initiation, and periodically thereafter. Dose adjustments of warfarin should be made as medically indicated.

Patients are discouraged from taking proton pump inhibitors or other strong anti-acids (e.g., H-2 antagonists) as these may interfere with the reliable identification of the R2PD.

7.7.1. CYP3A inducers

Avoid the concomitant use of strong CYP3A inducers, including St John's wort (see [ATTACHMENT 2](#), a list of common CYP3A inhibitors and inducers).

7.7.2. CYP3A and UGT inhibitors

Although pexidartinib does not appear to inhibit cytochrome P450 (CYP) drug-metabolizing enzymes to an important extent, caution is warranted when administering pexidartinib to subjects taking drugs that are highly dependent on CYP for metabolism and have a narrow therapeutic index. It is not known whether systemic exposure to these medications will increase while subjects are receiving pexidartinib.

Of the five major CYP isoforms, 3A4 (BFC) may be involved in Phase 1 metabolism of PLX3397, with possibly CYP1A2 playing a minor role (see [ATTACHMENT 2](#) for a list of common CYP3A inhibitors and inducers). In general, strong inducers of CYP3A4 should be avoided unless absolutely clinically necessary. These include anticonvulsants, mycin,

antimicrobials, and antiretrovirals. Some common examples include inducers such as rifampicin, carbamazepine, phenytoin, efavirenz, and nevirapine.

Avoid concomitant use of pexidartinib with moderate or strong CYP3A inhibitors or UGT inhibitors. If concomitant use with a moderate or strong CYP3A inhibitor or UGT inhibitor cannot be avoided, reduce the pexidartinib dose according to the recommendations in Table 7.3. If concomitant use of a moderate or strong CYP3A inhibitor or UGT inhibitor is discontinued, increase the pexidartinib dose (after 3 plasma half-lives of the moderate or strong CYP3A inhibitor or UGT inhibitor) to the dose that was used before starting the inhibitor.

Table 7-3: Recommended Dosage Reductions for Pexidartinib with Concomitant Use of Moderate or Strong CYP3A Inhibitors or UGT Inhibitors

Current Total Daily Dose	Modified Total Daily Dose	Administration of Modified Total Daily Dose
800 mg	400 mg	200 mg twice daily
600 mg	400 mg	200 mg twice daily
400 mg	200 mg	200 mg once daily

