5.0 STUDY DESIGN

5.1. Overview of Study Design

This Phase I/II, open label, multicenter study includes a dose evaluation portion (Pilot phase) in which the safety profile of PLX3397 as a single oral agent will be evaluated, followed by an expansion cohort (Phase II) in which the efficacy and safety of PLX3397 administered at the RP2D will be evaluated in patients with unresectable stage III or stage IV KIT-mutated melanoma (comprising mainly acral, mucosal or CSD forms of the disease).

The Pilot portion of the study follows a 3+3 design to determine if 1000 mg per day is an appropriate dose for the Phase II portion. Three patients are planned to be dosed initially. If 0 or

1 of 3 patients at the 1000 mg dose level cohort experience dose-limiting toxicity (DLT), 3 additional patients will be enrolled for a total of 6 patients. If ≥ 2 of 6 patients experience DLT at the 1000 mg dose, the dose will be de-escalated to 800 mg per day. If 0 or 1 of 3 patients at the 800 mg dose level cohort experiences DLT, 3 additional patients will be enrolled for a total of 6 patients. If ≥ 2 of 6 patients experience DLT at the 800 mg dose, the study will be terminated due to intolerability. Additional patients may be enrolled in a dose cohort based on safety and efficacy observations. The RP2D can be either 1000 mg per day or 800 mg per day based on discussions between the Sponsor and the investigators. The RP2D will be further evaluated in an expansion cohort during the Phase II portion of the study.

In the Phase II portion of the study, an analysis of anti-tumor response will be carried out after approximately 13 patients have been treated. If 3 or more responses (23%) are seen (complete response (CR) and partial response (PR) based upon Response Evaluation Criteria in Solid Tumors (RECIST) v1.1 or PET imaging), an additional approximately 19 patients will be enrolled and treated.

As of June 30 2018, 6 patients were enrolled in the Pilot portion of the study and received 1000 mg per day dose. Two subjects are currently ongoing. Following a preliminary safety and efficacy assessment of these 6 patients, the sponsor decided to discontinue this study. The sponsor informed the 2 remaining subjects of study discontinuation and re-consented the subjects to continue in the extension part of the study.

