6.1. Inclusion Criteria

Each patient must meet all of the following inclusion criteria to be enrolled in the study to treatment:

1. Age ≥ 18 years
2. Unresectable stage III or stage IV melanoma which is histologically confirmed at the treating institution with KIT mutation(s) not known to be resistant to PLX3397.

Note: Patients with KIT exon 8, 9, 11, 13, and 14 mutations are the most likely to be sensitive to PLX3397. Patients with KIT exon 17 or 18 mutations D816V, Y823D, and A829P should not be enrolled as they are not sensitive to PLX3397. Other KIT exon 17 or 18 mutations may be sensitive to PLX3397 and should be enrolled.

3. No limit on prior systemic therapies for melanoma. Patients who have not received prior therapy are eligible if they have a potentially sensitive KIT mutation.
4. Presence of measurable lesions by RECIST v1.1
5. Eastern cooperative oncology group (ECOG) performance status 0, 1, or 2
6. Life expectancy ≥ 3 months in the judgment of the investigator
7. Adequate organ and bone marrow function
 - a. Absolute neutrophil count (ANC) $\geq 1.5 \times 10^9/L$, Hgb ≥ 10 g/dL, platelet count $\geq 100 \times 10^9/L$
 - b. AST/ALT $\leq 2.5 \times$ upper limit of normal (ULN) or $< 5 \times$ ULN in the presence of liver metastases, total bilirubin ≤ 1.5 ULN (unless due to Gilbert's Syndrome, in which case it must be ≤ 2.5 mg/dL), albumin ≥ 3.0 g/dL
 - c. Serum creatinine $\leq 1.5 \times$ ULN or calculated creatinine clearance (CrCl) > 60 mL/min using the Cockcroft-Gault formula

Patients may be transfused or receive granulocyte-colony stimulating factor (G-CSF) or growth factors.

8. Women of child-bearing potential must have a negative serum pregnancy test at Screening and must agree to use an effective form of contraception from the time of the negative pregnancy test up to 3 months after the last dose of study drug. Effective forms of contraception include abstinence, hormonal contraceptive (injectable or implantable) in conjunction with a barrier method, or a double barrier method. Women of non-child-bearing potential must have been postmenopausal for ≥ 1 year or surgically sterile.
9. Fertile men must agree to use an effective method of birth control during the study and for up to 3 months after the last dose of study drug.
10. Willingness and ability to provide written informed consent prior to any study-related procedures and to comply with all study requirements

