7.8. Dosage Modification for Renal Impairment

The recommended dosage of pexidartinib for patients with mild to severe renal impairment (CL_{cr} 15 to 89 mL/min estimated by Cockcroft-Gault using actual body weight) is 200 mg in the morning and 400 mg in the evening.

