8.3. Treatment Group Assignments

This is an open-label, sequential dose-escalation study with an expansion cohort. The initial dose level of PLX3397 will be 1000 mg/day administered BID. Thereafter, dose de-escalation will occur as described in Section 7.2.1. The expansion cohort will be enrolled at the RP2D according to inclusion and exclusion criteria (Section 6.1 and Section 6.2).

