9.1.12. Extension phase

Subjects receiving clinical benefit (SD, PR, or CR) from study treatment at the time of data cut-off of the main study, will be offered the opportunity to continue pexidartinib treatment in an extension phase.

Procedures to be performed before the morning dose in the extension phase include:

- Physical examination (symptom-directed)
- Serum chemistry: sodium, potassium, chloride, CO₂, calcium, phosphorus, glucose, BUN, creatinine, uric acid, total protein, albumin, total and direct bilirubin, AST, ALT, alkaline phosphatase, GGT, and LDH;
- Hematology: hemoglobin, hematocrit, white blood cell count with a differential, platelet count
- Vital signs: blood pressure, respiratory rate, pulse rate, and body temperature;
- Adverse event assessment
- Study drug compliance via study drug diary review and accountability
- CT chest, abdomen, and pelvis (performed every 12 weeks) (PET/CT scan may be used as well)

Subjects will continue in the extension phase until disease progression, unacceptable toxicity or withdrawal of consent.

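### Table 7-3 has no row for 1000 mg/day, so the dose reduction required with an unavoidable CYP3A or UGT inhibitor is undefined at the study's own starting dose

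*Combined protocol and SAP*

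**What the plan says.** Section 7.7.2, listed among the sections updated in version 9.0, tells sites first to avoid moderate or strong CYP3A inhibitors and UGT inhibitors. If a moderate or strong CYP3A "inhibitor or UGT inhibitor cannot be avoided, reduce the pexidartinib dose according to the recommendations in Table 7.3". Table 7-3 has three rows: 800 to 400, 600 to 400, and 400 to 200 mg/day. When the inhibitor is stopped, the subject returns to the previous dose after three half-lives of the inhibitor.

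Section 7.2.1 sets "Cohort 1: 1000 mg/day (400 mg in the morning and 600 mg in the evening". The only lower cohort is 800 mg/day. Section 5.1 reports that "6 patients were enrolled in the Pilot portion of the study and received 1000 mg per day dose", that two were ongoing as of 30 June 2018, and that the sponsor discontinued the study and re-consented those two for the extension.

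Section 7.8, also updated in version 9.0, gives a recommended dosage for renal impairment: clearance of "15 to 89 mL/min estimated by Cockcroft-Gault using actual body weight) is 200 mg in the morning and 400 mg in the evening", that is, 600 mg/day.

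For the extension, Section 9.1.12 opens its list with "Procedures to be performed before the morning dose in the extension phase include". The list has serum chemistry, which includes creatinine. Its only bedside measurements are "Vital signs: blood pressure, respiratory rate, pulse rate, and body temperature". It contains no weight and no concomitant-medication review. The extension column of Table 2-1 agrees: weight is scheduled only at Screening and End of Study, and concomitant medications are blank in that column.

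**The concern.** A dose-reduction rule that omits the protocol's own starting dose leaves the site without a number in the case where exposure would be highest. The rule covers the way back up after the inhibitor stops, but not the way down from 1000 mg/day. The case is plausible, since Attachment 2 lists clarithromycin, fluconazole, ciprofloxacin and verapamil among the inhibitors.

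What is at stake is liver safety. Section 3.1.2 reports transaminase rises in about half of patients at 600 mg/day or more. Section 3.3 warns that liver injury can be fatal and reports one death with cholestatic injury still ongoing. The stated purpose of version 9.0 was to update safety information and revise the dose-modification criteria, so the gap lies within that amendment's own scope.

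A second, smaller matter follows. The 7.7.2 rule works only if the site knows of a new inhibitor, and the 7.8 rule only if it has a current weight. The extension visits schedule neither.

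**Working it through.** The plan states no figure for this case that could be reproduced. The check is a look-up of each protocol dose in Table 7-3, followed by dose arithmetic.

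**1. Look-up.** Inputs: Table 7-3, and the 200 mg capsule strength in Section 7.1.

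| Current mg/day | Table 7-3 gives | Share kept | Half | Half, rounded up to whole capsules |
|---|---|---|---|---|
| 1000 | no entry | – | 500 | 600 |
| 800 | 400 | 400/800 = 0.50 | 400 | 400 |
| 600 | 400 | 400/600 = 0.67 | 300 | 400 |
| 400 | 200 | 200/400 = 0.50 | 200 | 200 |

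The share kept is not constant, so no single ratio gives a value for 1000. Halving and rounding up to whole capsules fits all three rows and would give 600 mg/day. That pattern is an inference; the protocol does not state it.

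**2. The two whole-capsule candidates.** 400/1000 = 0.40 and 600/1000 = 0.60. Only 0.60 lies within the table's range of 0.50 to 0.67.

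The documents give no fold change in exposure with an inhibitor. Assume 1.5 to 2.0, the inverse of the table's ratios. In mg/day equivalents without an inhibitor:

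- 1000 left unreduced: 1000 × 1.5 to 1000 × 2.0 = 1500 to 2000
- 600: 900 to 1200
- 400: 600 to 800

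Of the two candidates, only 400 stays at or below 1000 over the whole assumed range; 600 does so up to 1000/600 = 1.67-fold. However, the table does not apply that test to itself. Its 600 mg row gives 400, which becomes 600 to 800, at or above the current dose. So 400 is the cautious choice, 600 is the choice that matches the table's pattern, and the documents do not decide between them.

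**3. Does weight matter to 7.8?** Cockcroft-Gault as in Attachment 1, with an illustrative man aged 55 and creatinine 0.9 mg/dL:

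- At 70 kg: (140 − 55) × 70 / (72 × 0.9) = 5950 / 64.8 = 91.8 mL/min, outside the 7.8 band.
- Weight at which clearance is 89: 89 × 64.8 / 85 = 67.8 kg. That is a loss of 2.2 kg, or 2.2/70 = 3.1%.

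A small weight change can therefore move a subject into the 600 mg/day band. For a subject on study on 30 June 2018 and still on drug at the date of version 9.0 (25 January 2020), the last scheduled weight was the Screening one. It was then at least 574 days old (574/28 = 20.5 cycles).

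**4. Who is reached.** One 200 mg/day reduction takes a subject from 1000 to 800, which the table covers. If 7.8 replaces the assigned dose, a subject with clearance of 15 to 89 mL/min is on 600, which is also covered. What remains is a subject still on 1000 mg/day, above the 7.8 band, who needs an inhibitor.

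**The case against.** The best defence is that the gap is narrow and has safeguards. Avoiding inhibitors is the first instruction. Section 7.5 requires the Medical Monitor to be notified of dose adjustments and leaves room for clinical judgment on toxicity. A short inhibitor course could be handled by holding the drug, since 7.5 generally ends participation only after interruptions longer than two weeks. All of this stands and limits the consequence. A reader might infer that the site is forced to pick 400 or 600 mg/day; it is not, because holding is possible. But notification does not supply a dose, and 7.7.2 tells the site to reduce without saying to what.

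Four stronger readings are tempting, and the documents do not support them:

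- **That the table implies 400 mg/day.** It does not; its pattern points to 600, and the exposure argument for 400 rests on an assumed fold change.
- **That 7.8 conflicts with the assigned dose or with the 800 mg/day floor in 3.2.** Section 7.8 is headed as a dosage modification and reads naturally as replacing the assigned dose. The 3.2 sentence concerns which doses are evaluated as cohorts. Only its application to subjects already on treatment could be stated more plainly.
- **That clearance cannot be computed in the extension.** Attachment 1 lists creatinine clearance within serum chemistry, which is done every 28 days, and a site may weigh the subject unprompted. The 574 days are the age of the last scheduled weight, not evidence that it would be used. Likewise, the duty in 7.7 to record concomitant treatment remains.
- **That DLT evaluability or the Phase II response rate is affected.** All six Pilot patients were enrolled before version 9.0, and the sponsor discontinued the study.

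It is also fair that the extension was meant to reduce procedures (Section 3.2), so adding items has a cost.

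**Conclusion.** The point holds as a minor drafting omission. The reduction that 7.7.2 calls for is undefined at 1000 mg/day, the starting dose and the only one reported as given, and no other section supplies it. Separately, the extension visits do not schedule two inputs on which 7.7.2 and 7.8 depend.

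The effect is limited to dosing safety for at most two known extension subjects. Their current dose and creatinine clearance are not stated, so possibly nobody is affected. The gap becomes live only if a subject remains on 1000 mg/day and needs an inhibitor that cannot be avoided. That conclusion needs no assumption about exposure; the assumed 1.5- to 2-fold range bears only on the choice between 400 and 600 mg/day, which is left to the sponsor. No analysis or study conclusion changes.

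**What to change.** Add a 1000 mg/day row to Table 7-3 with a whole-capsule dose that the sponsor sets from its PK data: 400 mg/day is the conservative option, and 600 mg/day follows the halve-and-round-up pattern. Alternatively, state that a subject on 1000 mg/day must have the drug held, or be reduced first to a listed dose.

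Add weight and a concomitant-medication check to Section 9.1.12 and to the extension column of Table 2-1.

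Two editorial clarifications could go into the same amendment: say in 7.8 that it applies to subjects already on treatment, and correct the 7.5 reference to Table 7-2 as a source of dose reductions, since that table covers liver evaluation and restart and lists no reductions.

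The cost is one table row and two simple items at existing 28-day visits, a small burden in a phase designed to have fewer procedures, plus one clause and one cross-reference for the editorial points.
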